Because ASP015K is an immunosuppressive agent, it may increase the risk of infections and reactivation of latent, chronic infections. In particular, excessive immunosuppression can lead to serious infections. Of note is the fact that Xeljanz[®] (tofacitinib) 5 mg, a member of the class of JAK inhibitors to which ASP015K belongs, have been associated with new onset or aggravation of serious infections such as tuberculosis, pneumonitis, sepsis, viral infections, and opportunistic infectious diseases including fungal infections. In addition, several cases of malignant tumors have been reported, although their causal relation to the agent has not been established. Based on the data pooled from 5 domestic and overseas comparative studies of Xeljanz[®] (tofacitinib) 5 mg, the incidence density of malignancies (excluding non-melanoma skin cancers) among RA patients treated with 5 mg BID for a maximum of 1 year was 0.55/100 person-years (incidence rate 0.5% < 5/1216) [Xeljanz[®] Pharmaceutical Interview Form (in Japanese)].

These findings suggest that investigators pay particular attention to the possible development of infections and malignancies and take appropriate measures. Three cases of malignancies (stomach cancer, uterine sarcoma, chronic myelogenous leukemia) have been reported as of the cut-off date of 5 December 2013, from completed and ongoing national and international studies of ASP015K. Only the case of uterine sarcoma was judged as related to ASP015K.

In the Japanese clinical trial in patients with moderate to severe RA (015K-CL-RAJ1), 50 mg and higher doses of ASP015K significantly improved the ACR20 response rate versus placebo. Xeljanz[®] (tofacitinib) 5 mg, which acts via the same mechanism as ASP015K, was approved by the US FDA in 2012 for the treatment of adult patients with moderate to severe RA who had an inadequate response to or are intolerant of MTX. In March 2013, Xeljanz[®] (tofacitinib) 5 mg tablets was authorized for marketing in Japan for treating RA patients who had an inadequate response to conventional therapies. Therefore, a potential benefit of JAK inhibitor ASP015K is to improve RA.

One can also expect that long-term use of ASP015K will improve QOL of RA patients by successfully controlling the RA disease activity over an extended period.

- CONFIDENTIAL -

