 12. Any of the following laboratory values during the screening test period:
 - Hemoglobin < 9.0 g/dL
 - Absolute neutrophil count < 1000/ μ L
 - Lymphocyte count < 800/ μ L
 - Platelet count < 75000/ μ L
 - ALT $\geq 2 \times$ ULN
 - AST $\geq 2 \times$ ULN
 - Total bilirubin (TBL) $\geq 1.5 \times$ ULN
 - Estimated GFR ≤ 40 mL/min as measured by the MDRD method
 - β -D-glucan ≥ 11 pg/mL
 - Positive HBs antigen, HBc antibody, HBs antibody or HBV-DNA quantitation (However, subject with negative HBs antigen and HBV-DNA quantitation, and positive HBc antibody and/or HBs antibody is eligible if HBV-DNA is monitored

- CONFIDENTIAL -

by HBV-DNA quantitation at every scheduled visit after initiation of study drug administration.)

- Positive HCV antibody

13. Subject has a history of or concurrent active tuberculosis (TB). Eligibility criteria for TB are tabulated below:

History of active TB	Chest x-ray (for TB)	TB infection ^{b)}	Exposure to patients with infective TB (interview)	Eligibility
Present	-	-	-	Not eligible
Absent	Abnormal (active)	-	-	Not eligible
	Abnormal (old) ^{a)}	-	Eligible	Eligible if prophylaxis is given ^{c)}
	Normal	Positive	Eligible	Eligible if prophylaxis is given ^{c)}
		Negative	Exposed	Eligible if prophylaxis is given ^{c)}
Not exposed	Eligible			

a) Old TB is evidenced if chest x-ray reveals pleural thickening, band-like shadow, and calcification ≥ 5 mm. Chest x-ray within 90 days prior to baseline may substitute the screening test.

b) T-spot or Quantiferon Gold test is of first priority. When the result is equivocal or invalid, retest including other test methods may be allowed. If a retest is not performed, criteria for positive results will be followed. When T-spot or Quantiferon Gold test is not feasible, tuberculin test will be performed. Tuberculin is defined as positive with a red spot covering an area of 20 mm or more or induration. Tests conducted within 90 days prior to baseline may be used for diagnosis.

c) Subject must receive or have received prophylaxis with isoniazid or rifampicin. Prophylaxis will be administered for 6 to 9 months, starting from at least 21 days prior to baseline.

14. Subject meets any of the following in terms of infections except for TB:

- History of or concurrent severe herpes zoster (associated with Hunt syndrome or having ulcerative lesions) or disseminated herpes zoster
- History of multiple recurrences (at least twice) of localized herpes zoster

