3.4 Discontinuation Criteria for Individual Subjects

A discontinuation is a subject who enrolled in the study and for whom study treatment is permanently prematurely discontinued for any reason.

The subject is free to withdraw from the study treatment and/or study for any reason and at any time without giving reason for doing so and without penalty or prejudice. The investigator is also free to terminate a subject's involvement in the study at any time if the subject's clinical condition warrants it.

The Appendix 4 entitled "Liver Safety Monitoring and Assessment" describes liver function tests raised that provide grounds for discontinuation. Refer to Appendix 4 concerning the measures to take for increases in liver function test parameters.

The investigator/sub-investigator should discontinue the study if any of the following occurs:

1. The subject withdraws consent.
2. The investigator/sub-investigator judges that the study drug is not sufficiently effective and the treatment method needs to be changed.
3. Symptomatic CPK elevation ($> 1.5 \times \text{ULN}$ accompanied with severe and unusual episodes of myalgia, muscular weakness, or muscle twitching).
4. Any case of myopathy involving severe and unusual episodes of myalgia, muscular weakness, or muscle twitching that persists for no less than, or aggravates rapidly within, 2 weeks, regardless of the CPK level.
5. A previously HBV-infected patient with positive HBe antibody, positive HBs antibody, or both has been shown positive for HBV-DNA during the study.
Attention should be paid that abrupt discontinuation of immunotherapy may cause fulminant or severe liver failure. Therefore, if the subject manifests HBV reactivation, the investigator/sub-investigator will administer nucleoside analogs without delay according to the "Proposal for Management of Rheumatic Disease Patients with Hepatitis B Virus Infection Receiving Immunosuppressive Therapy" (Japan College of Rheumatology). The investigator/sub-investigator will carefully decide whether to continue or discontinue the study drug and concomitant DMARDs in consultation with the hepatology specialist.
6. Malignant tumor
7. The subject develops a serious infection or other AEs, and continued administration of the study drug is not deemed appropriate in the subject's best interest by the investigator/sub-investigator.

- CONFIDENTIAL -

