Pregnancy testing will be performed from screening according to the Schedule of Assessments. Serum pregnancy testing is required only at screening, and urine pregnancy testing will be performed after baseline. The serum pregnancy testing will be performed by the central laboratory and the urine pregnancy testing will be performed by the study centers using the kits provided by the central laboratory. If, in the serum pregnancy test, hCG level exceeds ULN, but the possibility of pregnancy can be completely ruled out by another test, the subject is eligible for enrollment. Pregnancy testing is not subject to the safety assessment.

- If a urine pregnancy test is positive at any time, a negative serum pregnancy is required for the subject to continue participation in the study. If the possibility of pregnancy can be completely ruled out by another test, the subject may continue to participate in the study.
- The pregnancy tests need not be performed if the possibility of pregnancy can clearly be ruled out, such as if the woman is postmenopausal and has not had a menstrual period for 1 year or more, or has had a hysterectomy, bilateral oophorectomy, etc.

3) Tuberculosis test

The tuberculosis test will be performed at screening to confirm the eligibility of the subject in accordance with Exclusion Criterion 13. T-SPOT or QuantiFERON Gold test is the preferential test for tuberculosis infection. If T-SPOT or QuantiFERON Gold test cannot be performed, tuberculin skin test may be performed instead. Tuberculin test and QuantiFERON Gold test cannot be performed at the central laboratory.

Tuberculosis test is not required at screening provided that there is documentation of a negative tuberculosis test within 90 days prior to baseline.

4) Hepatitis test

Tests for HBs antigens, HBs antibodies, the HBV-DNA assay, HBc antibodies, and HCV antibodies will be performed at the screening visit to confirm the eligibility of the subject. If a subject is positive for either or both HBc antibodies and HBs antibodies, the subject will be monitored during the treatment period by performing an HBV-DNA assay at scheduled visits and early termination. Safety analysis will not be performed for the results of HBV-DNA assays from baseline.

- CONFIDENTIAL -

5) CPK monitoring

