APPENDIX <2>: LABORATORY TESTS

	Visit	Collecting tube	Parameters to be analyzed
Hematology	Screening, Baseline, Week 4, Week 8, Week 12, Week 16, Week 20, Week 24, Week 28, Week 32, Week 36, Week 40, Week 44, Week 48, Week 52, at early termination, follow-up, unscheduled	2 mL vacutainer tube containing EDTA-2K	Hemoglobin, hematocrit, RBC, WBC, differential WBC, platelet count
Biochemistry	Screening, Baseline, Week 4, Week 8, Week 12, Week 16, Week 20, Week 24, Week 28, Week 32, Week 36, Week 40, Week 44, Week 48, Week 52, at early termination, follow-up, unscheduled	9mL vacutainer tube containing the separating medium For glucose: 2 mL vacutainer tube containing NaF+EDTA-2Na For β -D-glucan: 3 mL container for blood endotoxin/ β -D-glucan	Na, K, Ca, Cl, Mg, HCO ₃ , BUN, phosphorus, glucose, creatinine, ALP, AST (GOT), ALT (GPT), γ -GTP, TBL, total protein, albumin, uric acid, CPK, LDH, serum amylase, eGFR, β -D-glucan
Biochemistry (at CPK monitoring)	At CPK monitoring	4 mL vacutainer tube containing the separating medium	CK-MB, troponin-T, aldolase
Fasting lipid profile test	Baseline, Week 12, Week 20, Week 28, Week 40, Week 52, at early termination, follow-up, unscheduled	(Included among biochemistry tests)	Total cholesterol, LDL, HDL, triglycerides
Tuberculosis test (When performed at the central laboratory)	Screening	10 mL vacutainer tube containing heparin Na	Interferon γ titer
Anti-CCP antibody, RF, hepatitis test	Screening	9 mL vacutainer tube containing the separating medium	Anti-CCP antibodies, RF, HBs antigens, HBs antibodies, HBc antibodies, and HCV antibodies
Hepatitis DNA test	Screening If a subject is positive for HBc antibodies or HBs antibodies, tests should be performed at the following visits: Baseline, Week 4, Week 8, Week 12, Week 16, Week 20, Week 24, Week 28, Week 32, Week 36, Week 40, Week 44, Week 48, Week 52, at early termination, follow-up, unscheduled	5 mL vacutainer tube containing the separating medium	HBV-DNA assay

- CONFIDENTIAL -

Urinalysis	Screening, Baseline, Week 4, Week 8, Week 12, Week 16, Week 20, Week 24, Week 28, Week 32, Week 36, Week 40, Week 44, Week 48, Week 52, at early termination, follow-up, unscheduled	For urinalysis: 10 mL light-blocking urine collection tubes For urine microscopic examination: 10 mL urine collection tubes	pH, specific gravity, protein, glucose, keton bodies, bilirubin, occult blood, sediment

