If a subject has an AE which has a missing severity, then the subject will be counted in the severity category of "Missing" (i.e., missing severity will not be imputed).
- Drug related TEAEs by severity
- Grade 3 or higher TEAEs by severity
- TEAEs by relationship to study drug  
Subjects reporting more than one TEAE for a given PT will be counted only once for that term in the most related category reported.  
TEAE with missing relationship to study drug missing will be counted as drug related. Moreover, any TEAE with missing relationship to study drug or reference drug was counted as drug related (probable).
- TEAEs leading to death
- TEAEs leading to permanent discontinuation of study drug
- Drug related TEAEs leading to permanent discontinuation of study drug
- Serious TEAEs leading to permanent discontinuation of study drug
- Drug related serious TEAEs leading to permanent discontinuation of study drug
- TEAEs excluding serious adverse events that equal to or Exceed a threshold of 5% in Any Treatment Group
- Most common TEAEs (> 5% in any treatment group)
- Most common serious TEAEs (> 5% in any treatment group)
- The number and percentage of subjects with TEAEs by subgroups defined in section 7.8

- The number and percentage of subjects with TEAEs of special interest.

Following adverse events of special interest are defined in the Appendix 10.8:

- Serious Infections
- Malignancies
- Herpes Zoster Related Disease (Herpes Zoster and Varicella)
- Herpes Zoster
- Varicella
- Infections That Require Intravenous Anti-infectious Therapy

In addition, the subgroup analysis of Sex, Age Group, Concomitant Steroid at Baseline, and Prednisone Dose at Baseline will be conducted.

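### No HBV-DNA conversion rate is planned among the antibody-positive subjects who are monitored, because the protocol bars safety analysis of the assay results and the SAP adds none

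*Protocol*

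**What the plan says.** Protocol 1.4 says of the drug that "it may increase the risk of infections and reactivation of latent, chronic infections". Exclusion criterion 12 (Protocol 3.3) would bar hepatitis B marker positivity, with one exception. A subject negative for HBs antigen and HBV-DNA but with "positive HBc antibody and/or HBs antibody is eligible if HBV-DNA is monitored" "by HBV-DNA quantitation at every scheduled visit after initiation of study drug administration".

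Protocol 5.4.4, item 4, repeats the requirement: "If a subject is positive for either or both HBc antibodies and HBs antibodies, the subject will be monitored during the treatment period". Protocol Appendix 2 gives the schedule under the words "If a subject is positive for HBc antibodies or HBs antibodies, tests should be performed at the following visits". The visits are baseline, every four weeks from Week 4 to Week 52, early termination, follow-up and unscheduled visits. Discontinuation criterion 5 (Protocol 3.4) concerns a previously infected subject who "has been shown positive for HBV-DNA during the study".

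Item 4 of 5.4.4 then closes with: "Safety analysis will not be performed for the results of HBV-DNA assays from baseline".

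The SAP is consistent with that sentence. Its laboratory section (7.5.2) covers hematology, chemistry, urinalysis and fasting lipids. HBV-DNA is in neither its table of selected laboratory variables nor the overview in Appendix 4. Hepatitis B serology is not among the baseline characteristics (7.2.2) or the subgroups (7.8). Reactivation is not an item of its own among the adverse events of special interest (Appendix 8).

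**The concern.** The protocol makes serial HBV-DNA testing a condition of entry for a defined group, acts on the result, and then excludes the result from safety analysis. This is a stated rule, not missing detail. If the plan is followed as written, the study report will contain neither the number of subjects monitored nor the number who converted, so it will contain no rate among them.

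The SAP treats comparable items differently. β-D-glucan, which has its own suspension criterion (Protocol 3.4.1.1), gets a shift-from-baseline analysis (SAP 7.1). Herpes zoster gets patient-year rates with confidence intervals (SAP 7.5.1.2). Chest radiographs and pregnancies at least get subject listings (SAP 7.5.5 and 7.5.6).

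At stake is what a trial with 52 weeks of treatment can say about a risk it names in its own risk-benefit section. A percentage over a whole arm mixes subjects who were tested repeatedly with subjects whose HBV-DNA was not followed.

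**Working it through.** **Where a conversion would and would not appear**

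- Assay results: excluded by Protocol 5.4.4, with no table or listing in the SAP.
- Adverse events: Protocol 5.5.1 makes a test abnormality an adverse event if it causes signs or symptoms, needs active intervention, needs study drug to be suspended, interrupted or discontinued, or is judged clinically significant. Criterion 5 calls for nucleoside analogs on reactivation, so a treated reactivation qualifies. A positive assay that the site does not regard as reactivation might not.
- Denominator: adverse events are summarised on the SAF, which is every treated subject (SAP 5.3).
- Number monitored: reported nowhere.

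**Size, as an illustration only**

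The documents contain no figure to reproduce. The planned arm is 170 (Protocol 7.1). The antibody-positive share *s* is not given, so 10%, 20% and 30% are assumed:

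- 170 × 0.10 = 17
- 170 × 0.20 = 34
- 170 × 0.30 = 51

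If conversions are found only in tested subjects, the whole-arm percentage equals the percentage in monitored subjects multiplied by *s*. The rate is therefore diluted by 1/*s*: 10-fold, 5-fold or 3.3-fold.

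With zero events, the exact (Clopper-Pearson) two-sided 95% upper limit is 1 − 0.025^(1/n). With two events, the estimate is 2/n with the Clopper-Pearson interval.

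| Denominator n | Upper limit, 0 events | Estimate (95% CI), 2 events |
|---|---|---|
| 17 (assumed) | 19.5% | 11.8% (1.5 to 36.4) |
| 34 (assumed) | 10.3% | 5.9% (0.7 to 19.7) |
| 51 (assumed) | 7.0% | 3.9% (0.5 to 13.5) |
| 170 (whole arm) | 2.1% | 1.2% (0.1 to 4.2) |

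**Unequal time on drug**

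Placebo subjects start ASP015K at Week 12 or Week 28 (Protocol 5.1.1). Full-course ASP015K exposure is therefore 52 weeks, 52 − 12 = 40 weeks or 52 − 28 = 24 weeks. A simple percentage over all ASP015K exposure would treat these as equal.

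**The case against.** The strongest reply is that the sentence excludes assay results, not the events they lead to. This largely stands. A reader might infer that reactivations will never be reported, and the documents do not support that. A conversion that leads to antiviral treatment or stopping of study drug is an adverse event by the protocol's definition. It would appear in the tables by system organ class and preferred term, in the by-subject listings and, if drug is stopped, in the discontinuation summaries (SAP 7.2.1, 7.5.1 and 7.5.1.1). The DSMB also reviews unblinded safety data (Protocol 10.1).

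Nor would it be right to say that reactivation can enter no special-interest category. Appendix 8 takes every serious event in the infections class, and "Infections That Require Intravenous Anti-infectious Therapy" covers those treated intravenously. Hepatic consequences are tabulated separately under SAP 7.5.2.1.

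A further reply is that the SAP attaches no confidence interval to adverse event percentages. That is correct. The 2.1% limit on 170 is what a reader might work out from a zero count; it is not a planned output.

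Finally, the data are collected, so the rate could be produced later. That is true, but it leaves the choice of denominator, of what counts as positive and of time window until after unblinding. None of these replies supplies a rate among the monitored subjects.

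**Conclusion.** The point holds as a reporting gap. Neither document plans a conversion rate, or any display of HBV-DNA results, for the antibody-positive subjects who must be tested. Events reach the report only through adverse event recording and over all treated subjects.

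The size depends on an antibody-positive share that the documents do not state. Over an assumed 10% to 30%, zero events would leave upper limits of 19.5% to 7.0% in monitored subjects, against 2.1% on a whole arm.

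Two limits apply. The documents identify these as the subjects monitored; they do not establish that nobody else is at risk. The gap also does not affect the primary endpoints, the testing sequence or the monitoring itself. It should be fixed because it limits what the trial can conclude about a risk it names.

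**What to change.** Delete the quoted sentence from Protocol 5.4.4. Add two items to SAP 7.5.2:

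1. A subject listing of all HBV-DNA results.
2. A table on SAF subjects who are HBc and/or HBs antibody positive and HBV-DNA negative at both screening and baseline. It shows n/N with any post-dose positive HBV-DNA and an exact two-sided 95% CI. The documents set no threshold for a positive result, so the table should name the central laboratory's own reporting category.

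Present the table for Weeks 0 to 12 by randomised group, and for all ASP015K exposure by the treatment being taken at the positive test. For the latter, add a rate per 100 patient-years following Definition 1 of SAP 7.5.1.2, with time counted from the first ASP015K dose. That section's interval formula uses log(A/T) and 1/A, which are undefined when A = 0, so use exact Poisson limits.

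The cost is one protocol sentence, one listing and one table, with no new sampling. The drawback is small denominators and wide intervals.

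Separately, the statements of discontinuation criterion 5 should be reconciled. The Synopsis names HBc antibody where Protocol 3.4 reads HBe; check this against the source PDF in case it is a text-reading error. In both places the criterion sits in a list of reasons to discontinue, while its own text leaves continuing or stopping to a case-by-case decision with a specialist. No clinical rule is proposed here.

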5.4.4.1 CPK Monitoring

If a CPK elevation is observed after administration of the study drug begins, CPK will be monitored as follows.

- If laboratory testing reveals $CPK > 3 \times ULN$, and the subject is asymptomatic, retest CPK preferably within 1 week of previous blood sampling to confirm it. Subsequently, retest CPK weekly (from the date of the initial CPK elevation) until $CPK \leq 3 \times ULN$ or is stable according to the judgment of the investigator/sub-investigator. If the retest cannot be performed within 1 week of blood sampling, which marks the starting point of CPK monitoring, suspension or interruption of the study drug should be considered until the retest results are obtained.
- In subjects whose baseline CPK is already $> 3 \times ULN$, if laboratory testing reveals $CPK > 2 \times$ baseline, and the subject is asymptomatic, retest CPK preferably within 1 week of previous blood sampling to confirm it. Subsequently, retest CPK weekly (from the date of CPK elevation to $> 2 \times$ baseline) until $CPK \leq 2 \times$ baseline, or is stable in the judgment of the investigator/sub-investigator. If the retest cannot be performed within 1 week of blood sampling, which marks the starting point of CPK monitoring, suspension or interruption of the study drug should be considered until the retest results are obtained.
- If CPK is $> 10 \times ULN$ at any time, treatment will be immediately suspended or interrupted (see Section 3.4 Discontinuation Criteria for Individual Subjects), and retest CPK.
- If there is a symptomatic CPK elevation (CPK elevation $> 1.5 \times ULN$ accompanied by severe and unusual episodes of myalgia, muscular weakness, or muscle twitching), as reported by the investigator/sub-investigator, treatment will be immediately discontinued (see Section 3.4 Discontinuation Criteria for Individual Subjects).

In the retest for CPK monitoring, the following tests will be performed in addition to CPK measurements. The content of the subject questionnaire will be entered in the eCRF.

- Laboratory tests
(Measurement parameters: CK-MB, troponin T, aldolase)
- A targeted physical examination* and subject questionnaire to assess muscle strength and pain
*: As part of the targeted physical examination, urinalysis (blood and microscopy) will be performed.

- CONFIDENTIAL -

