1.4 Risk-Benefit Assessment

Findings from nonclinical studies of ASP015K suggest that the primary areas of toxicity are the gastrointestinal system, hematopoietic system, and muscle tissue. The commonly observed AEs during clinical studies conducted to date included reversible neutrophil count decreased, gastrointestinal disorders (e.g., diarrhoea, nausea, flatulence, vomiting), CPK elevations without evidence of myopathy, and headache. In the clinical trial of ASP015K in Japanese patients with RA (015K-CL-RAJ1), 1 or more groups reported rheumatoid arthritis, nasopharyngitis, blood creatine phosphokinase increased, diarrhoea, cystitis, constipation,

- CONFIDENTIAL -

stomatitis, dyspepsia, lipids increased, and blood triglycerides increased at incidence rates of $\geq 5\%$. By the MedDRA System Organ Class (SOC), Infections and infestations, Gastrointestinal disorders, Musculoskeletal and connective tissue disorders, and Investigations showed high incidence rates. Thus, these events may occur in the present study.

In the 015K-CL-QT01 study to evaluate the effect of ASP015K on cardiac function (QT interval), single doses of ASP015K 150 mg and 450 mg shortened the QTcF interval (QT interval corrected using Fridericia's Correction). The maximum decrease in the mean change from placebo- and baseline-adjusted QTcF occurred at 2 and 4 hour post dose with values of -12.0 and -14.7 msec for the 150 mg and 450 mg treatments, respectively. Therefore, shortened QT interval may be observed in the present study. The risk of drug-induced QT shortening is uncertain.

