If an increase in CPK is observed, in accordance with Section 5.4.4.1 CPK Monitoring, when CPK is retested, CPK, CK-MB, troponin T, and aldolase should also be tested. Urinalysis (blood and microscopy) will be performed as part of the targeted physical examination.

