5.4.4.2 Hepatic Function Abnormal

If laboratory testing for a subject enrolled in the study and receiving the study drug reveals an increase in serum aminotransferase (ALT, AST) $> 3 \times \text{ULN}$ or TBL $> 2 \times \text{ULN}$, at least 4 parameters (ALT, AST, ALP, and TBL) of the usual hepatic function test parameters should be retested. The retest should be performed between 48 hours and 72 hours after notification of the test results.

For additional information on monitoring and the assessment of the hepatic function test, see Appendix 4 “Liver Safety Monitoring and Assessment.”

If laboratory testing for a subject enrolled in the study receiving the study drug reveals an increase in serum aminotransferase (ALT, AST) $> 3 \times \text{ULN}$ and TBL $> 2 \times \text{ULN}$, the investigator will determine whether it is an SAE. Even if the abnormality is not considered an SAE by the investigator/sub-investigator, it will be reported to the sponsor or CRO in writing as in the case of SAEs.

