APPENDIX <4>: LIVER SAFETY MONITORING AND ASSESSMENT

If laboratory testing for a subject enrolled in the study and receiving the study drug reveals an increase in serum aminotransferase (ALT, AST) $> 3 \times \text{ULN}$ or TBL $> 2 \times \text{ULN}$, the investigator/sub-investigator should repeat at least 4 parameters (ALT, AST, ALP, and TBL) of the usual hepatic function test parameters. Retesting should be performed between 48 hours and 72 hours after notification of the test results. For studies for which a central laboratory () is used, alerts will be generated by the central laboratory regarding moderate and marked liver abnormality to inform the investigator or other responsible personnel and the sponsor. Subjects should be asked if they have any symptoms suggestive of hepatobiliary dysfunction by the investigator/sub-investigator.

Definition of Hepatic Function Abnormal

Confirmed hepatic function abnormal will be characterized as moderate (hepatocellular failure type or cholestasis type) or marked (mixed type) based on the ULN as follows:

	ALT or AST		TBL
Moderate			
Hepatocellular failure type	$> 3 \times \text{ULN}$	or	$> 2 \times \text{ULN}$
or			
cholestasis type			
Marked			
Mixed type	$> 3 \times \text{ULN}$	and	$> 2 \times \text{ULN}$

In addition, the subject with any of the following should be considered to have marked (severe) hepatic function abnormal.

ALT or AST $> 8 \times \text{ULN}$

ALT or AST $> 5 \times \text{ULN}$ for more than 2 weeks

ALT or AST $> 3 \times \text{ULN}$ and INR > 1.5

ALT or AST $> 3 \times \text{ULN}$ with the appearance of fatigue, nausea, vomiting, right upper quadrant pain or tenderness, pyrexia, rash and/or eosinophilia ($> 5\%$)

If the investigator/sub-investigator determines that abnormal liver function results, other than as described above, qualify as moderate or marked abnormalities, they should conduct additional monitoring and follow-up.

Follow-up Procedures

Confirmed moderate and marked hepatic function abnormal should be thoroughly characterized by obtaining appropriate expert consultations, detailed pertinent history, physical examination and laboratory tests by the investigator/sub-investigator. The investigator should complete the liver abnormality case report form (LA-CRF) or an appropriate document. Subjects with confirmed abnormal liver function test results should be followed as described below by the investigator/sub-investigator.

- CONFIDENTIAL -

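### As worded, Section 5.4.4.1 calls for the early CPK retest and muscle work-up only in asymptomatic subjects, so non-severe muscle symptoms with CPK up to 10 × ULN fall under no mandatory rule

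*Protocol*

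**What the plan says.** Protocol Section 5.4.4.1 has four rules for a CPK elevation after dosing starts.

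1. CPK above 3 × ULN: "and the subject is asymptomatic, retest CPK preferably within 1 week of previous blood sampling to confirm it". Retesting is then weekly until CPK is back to 3 × ULN or below "or is stable according to the judgment of the investigator/sub-investigator".
2. Baseline CPK already above 3 × ULN and a value above 2 × baseline: the same retest, with the same condition on symptoms.
3. CPK above 10 × ULN: suspend or interrupt treatment and retest, whatever the symptoms.
4. Symptomatic CPK elevation, defined as CPK above 1.5 × ULN with "severe and unusual episodes of myalgia, muscular weakness, or muscle twitching": discontinue.

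The work-up belongs to the retest. Section 5.4.4.1 lists CK-MB, troponin T, aldolase, a targeted examination with urinalysis and a "subject questionnaire to assess muscle strength and pain" as things done at it. Section 5.4.4, item 5, says that "when CPK is retested, CPK, CK-MB, troponin T, and aldolase should also be tested", and refers back to 5.4.4.1 for when that happens.

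The liver rule in Section 5.4.4.2 has no symptom condition. At ALT or AST above 3 × ULN, at least four "of the usual hepatic function test parameters should be retested". Under Appendix 4 the same enzyme level "with the appearance of fatigue, nausea, vomiting, right upper quadrant pain or tenderness, pyrexia, rash" moves the case up to the marked category.

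**The concern.** Rules 1 and 2 require the subject to be asymptomatic, and rule 4 requires severe and unusual symptoms. Mild or moderate myalgia or weakness satisfies neither. Below the 10 × ULN limit of rule 3, such a subject has no mandatory early retest and no work-up. The ordering is then inverted: a questionnaire on muscle strength and pain is called for in subjects who report no symptoms and not in those who report some, at the same CPK. The liver rules go the other way.

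The subject matter deserves a clear rule. Section 1.4 says that in the nonclinical studies "the primary areas of toxicity are the gastrointestinal system, hematopoietic system, and muscle tissue". Section 1.3 reports CPK increase as an adverse event in the Phase IIb study RAJ1 in 7 subjects (12.1%) at 150 mg, 1 (1.8%) at 100 mg and none on placebo. Section 2.2.2 accepts that individual CPK monitoring will be needed. RAJ1 gave the drug alone for 12 weeks; this trial gives it with MTX for up to 52 weeks.

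**Working it through.** **Coverage.** The table crosses the CPK bands with the symptom states, using only the four rules of Section 5.4.4.1 (baseline CPK not raised).

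| CPK | No symptoms | Non-severe muscle symptoms | Severe and unusual |
|---|---|---|---|
| > 1.5 to 3 × ULN | no rule | no rule | discontinue (rule 4) |
| > 3 to 10 × ULN | early retest, weekly retests, work-up (rule 1) | **no rule** | discontinue (rule 4); no retest or work-up called for |
| > 10 × ULN | suspend or interrupt, retest, work-up (rule 3) | same | same, plus discontinue (rule 4) |

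Above 3 × ULN, the only cell with no rule at all is the middle one. Rule 2 leaves the same hole. It reaches CPK values of 10 × ULN or less only when baseline lies between 3 and 5 × ULN, because 2 × 5 = 10; above that, rule 3 takes over.

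**Could another provision fill the cell?**
- Section 5.4.4, item 5: applies once CPK is being retested, so it adds no trigger.
- Section 3.4, criteria 3 and 4: both need severe and unusual symptoms.
- Section 5.4.4, additional sampling, and Section 3.4.1.1, criterion 5: both at the investigator's judgment.
- Section 5.5.1: an abnormality that produces symptoms is an adverse event. Section 5.4.3 requires follow-up of unresolved events but gives no retest interval.
- Section 5.5.6, Follow-up of Adverse Events: listed in the contents, but its text is not in the copy reviewed, so it could not be checked.

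**Size of the delay.** Inputs are the visit days and ±7-day windows in Table 1 and the five-week limit in Section 5.1.6.
- Nominal gap to the next visit: 57 − 29 = 28 days.
- Shortest, with windows in opposite directions: 28 − 7 − 7 = 14 days.
- Longest: 5 × 7 = 35 days.
- For an asymptomatic subject: preferably within 7 days.

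**Retests at stake.** Weekly retests falling strictly before the next visit number at most 14/7 − 1 = 1, 28/7 − 1 = 3 and 35/7 − 1 = 4. The minimum is 1, because retesting may stop at the first result if CPK is 3 × ULN or below or is judged stable.

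**Severity of the affected band.** SAP Appendix 9, Table 24, puts CPK Grade 2 at > 2.5 to 5 × ULN and Grade 3 at > 5 to 10 × ULN. The band > 3 to 10 × ULN is the upper part of Grade 2 and all of Grade 3.

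**The case against.** The best reply is that the rule means something narrower than its ordinary wording. Symptomatic CPK elevation is defined in the same list, again in Section 3.4 criterion 3, and in the synopsis, so asymptomatic is naturally its complement. A wholly literal reading would exclude nearly everyone, since entry requires at least 6 tender and 6 swollen joints. The questionnaire on pain also suggests that retested subjects were expected to have some symptoms.

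This stands as an account of what was probably intended, and it is why the point is minor. It does not remove the defect. The condition is placed on the subject, not on the defined category of elevation, and the visible text never links the two. Elsewhere the protocol uses the word in its ordinary sense: Section 5.5.4 lists asymptomatic and mild symptoms as alternatives within Grade 1. With approximately 150 centres, each would have to infer the special meaning.

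It is also fair that safeguards remain: biochemistry at every scheduled visit, extra tests and suspension at the investigator's discretion, adverse event follow-up, and DSMB safety review. A reader might infer that these subjects go unmonitored. The documents do not support that; what is lost is only the requirement for the early retest and its work-up. Nor can the 12.1% be read as the number affected. Those are adverse event reports with no stated ULN threshold, and Section 2.2.2 reports no accompanying symptoms suggestive of rhabdomyolysis or myopathy.

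**Conclusion.** The point holds as a minor safety-wording defect. On ordinary wording, non-severe muscle symptoms remove the mandatory early retest and work-up at CPK above 3 and up to 10 × ULN (or above 2 × baseline within the same limit). The next CPK called for is then at the next visit, 14 to 35 days away, in place of preferably within 7 days. The number of subjects affected cannot be derived and is probably small.

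The conclusion assumes that asymptomatic carries its ordinary meaning as regards muscle symptoms, and that the unseen Section 5.5.6 does not set a retest interval. If either assumption fails, only a clarification is needed. A reader might also infer that the sponsor chose less surveillance for symptomatic subjects, or that the efficacy or safety analyses are compromised. Neither follows: the wording looks like a drafting slip, and no endpoint or analysis depends on it.

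**What to change.** In the first two bullets of Section 5.4.4.1, delete the opening five words of "and the subject is asymptomatic, retest CPK preferably within 1 week of previous blood sampling to confirm it". The retest and work-up then apply whatever the symptoms. Keep the suspension rule above 10 × ULN and the discontinuation rule for severe symptoms in force in addition.

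Deletion is better than substituting a phrase such as not meeting the symptomatic definition. The substitute would still leave subjects with severe symptoms, who are discontinued, without the marker tests and examination.

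Leave the first bullet otherwise unchanged. Limiting it to subjects with baseline at or below 3 × ULN would lose cover: with baseline 4.5 × ULN, a rise to 8.9 × ULN is below 2 × 4.5 = 9 × ULN and below 10 × ULN, so only the first bullet catches it.

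The cost is about 1 to 4 extra retests between visits in each of the few affected subjects. Section 5.8 gives 4 mL per assessment for the muscle markers, so 1 × 4 = 4 mL to 4 × 4 = 16 mL, plus the biochemistry draw for CPK itself. If the 9 mL biochemistry tube in Appendix 2 were filled each time (an assumption), the total would be 1 × 13 = 13 mL to 4 × 13 = 52 mL. Section 5.1.6 already obliges subjects to return promptly when a visit is instructed for CPK monitoring.
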